Hypothesis I-a: tDCS will be safe in AIS patients with no increased risk of symptomatic intracranial hemorrhage (SICH) within the 24-hour period after stimulation. Hypothesis I-b: tDCS will not increase the rates of asymptomatic intracranial hemorrhage, early neurological deterioration (NIHSS during the 24-hour period after stimulation), 90-day mortality, and all serious adverse events. Hypothesis I-c: Majority of AIS patients ($\geq 90\%$) will tolerate the tDCS by completing at least 75% of the stimulation period with no major stimulation related pain, discomfort and skin changes.

Specific Aim II: To determine the feasibility of delivering tDCS in AIS.

Hypothesis II-a: tDCS will be started more rapidly over the course of the study and in the last 10 patients median time from randomization to tDCS initiation will be ≤ 10 minutes.

Specific Aim III: To explore the potential imaging and clinical efficacy of tDCS in AIS.

This aim will be accomplished by measuring, in actively treated and sham patients:

- 1) Early and late penumbral salvage, defined as proportion of penumbral tissue on baseline multimodal MRI that does not proceed to infarct on 2-hour and 24-hour MRI (PWI);
- 2) Early and

late collateral enhancement, evidenced by reduced perfusion lesion volume on 2-hour and 24-hour perfusion-weighted MRI (PWI); **3)** Early and late reduction in infarct growth from baseline to 2-hour and 24-hour MRI; **4)** Early improvement in neurologic deficit (NIHSS at 24h); **5)** Improvement in final 3-month disability and quality of life (modified Rankin scale, AMC Linear Disability Scale, EQ-5D, and Barthel Index)

Impact

This in-hospital safety trial, in non-thrombectomy candidates in a closely-observed, Emergency Department and hospital settings, will identify tDCS dose regimens that are feasible, well-tolerated, and preliminarily safe in patients with acute ischemic stroke. Study finding will identify the most promising dose regimens to advance to phase 2b and pivotal phase 3 efficacy trials for two patient populations with pressing need for improved therapies: 1) thrombectomy ineligible patients (standalone neuroprotection), and 2) thrombectomy-eligible patients (bridging neuroprotection in prehospital and early ED-arriving patients).

B. Background and Significance

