Concomitant/Interval medications/procedures	✓	✓	✓	✓	✓	✓	✓	✓	✓

* Skin Inspection will be performed before each stimulation period

D.6.2. Baseline Evaluation

- Demographics (age, sex, race)
- Last known well time
- Past medical/surgical history including vascular diagnoses and risk factors (stroke, TIA, carotid stenosis, myocardial infarction, atrial fibrillation, peripheral arterial disease, hypertension, diabetes, dyslipidemia)
- Medications, including antithrombotics, antihypertensives, statins, anti-arrhythmics Family history of vascular disease;
- Tobacco (including timing, duration, amount), alcohol, and illicit drug use;
- Vital signs (systolic blood pressure, diastolic blood pressure, pulse, respiratory rate, oxygen saturation);
- Premorbid global disability (modified Rankin Scale);
- Neurological deficits severity (NIHSS);
- Laboratory results (CBC, platelet count, glucose, lyses, INR, PTT, LFTs).

D.6.3. During tDCS Treatment

- NIH Stroke Scale (NIHSS),
- Tolerability/AE Form – Technologist, Tolerability Questionnaire – Patient

D.6.4. Early (2 Hours) After tDCS

- NIHSS,
- Multimodal MRI/CT
- Interval serious adverse events
- Interval medications/procedures

D.6.5. Late (24 Hours) After tDCS

- NIHSS
- Multimodal MRI/CT
- Interval serious adverse events
- Interval medications/procedures

D.6.6. Day 4

- Modified Rankin Scale (mRS)
- Interval serious adverse events
- Interval medications/procedures

D.6.7. Day 30

- mRS (phone),
- Interval serious adverse events
- Interval medications/procedures

D.6.8. Day 90

- NIHSS,
- Modified Rankin Scale (mRS)
- AMC Linear Disability Scale (granular disability)
- Barthel Index (BI) (activities of daily living)
- EuroQol (EQ-5D) (health-related quality of life)
- Interval serious adverse events
- Interval medications/procedures

D.6.9. Imaging Assessments

- Baseline

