Follow-up MR or CT imaging will be obtained 2h and 24h post-stimulation (supported by Radiology Dept. research funds). MRI Imaging sequences will include DWI/FLAIR/GRE/PWI/CEMRA and CT imaging sequences will consist of NCCT/CTA/CTP. RAPID image processing software will be applied to the above images to quantify, at the baseline, 2h, and 24h time-points: 1) Ischemic Core volume, 2) Perfusion lesion volume, and 3) Penumbra volume (perfusion volume - core volume). From these values, the following measures will be constructed: 1) Early penumbra preservation: Volume of baseline penumbra tissue not progressing to ischemic core at 2h; 2) Penumbral salvage: Volume of baseline penumbra tissue not progressing to ischemic core at 24h; 3) Early collateral flow enhancement: Perfusion lesion volume at baseline – Perfusion lesion volume at 2h; 4) Sustained collateral flow enhancement: Perfusion lesion volume at baseline – Perfusion lesion volume at 24h; 5) Early infarct growth: Ischemic core lesion volume at 2h – Ischemic core lesion volume at baseline; and 6) Final infarct growth: Ischemic core lesion volume at 24h – Ischemic core lesion volume at baseline. Additional location and extent of ischemic injury at baseline, 2h, and 24h will be rated using the MRI ASPECTS scoring system, with regions considered involved if diffusion restriction is present in more than 20% of the region or CT ASCPETS.^{54,55} In patients receiving MRI, location and extent of FVH and GVH will be rated using the FVH-modified ASPECTS and GVH modified ASPECTS scales.⁵⁶

D.6.10 Adverse Events

D.6.10.1 Serious Adverse Events (SAEs)

All serious adverse events occurring during the 90 days of study participation will be recorded. A serious adverse event is any adverse event that is fatal, is life-threatening, is permanently or substantially disabling, requires or prolongs hospitalization, or requires medical or surgical intervention to prevent one of the above outcomes.¹⁹

D.6.10.2 Symptomatic intracranial hemorrhage

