E.3.5. Exploratory Efficacy Endpoints Analysis (Specific Aim 3)

E.3.5.1. Exploratory Imaging Biomarker Efficacy Endpoints

This study is underpowered to definitively determine efficacy, so all imaging efficacy analyses will be purely exploratory and descriptive. Imaging biomarker efficacy endpoints will be characterized in the active and sham patients, and in higher and lower dose tiers, using means and 95% confidence intervals. The six imaging efficacy endpoints of greatest interest that will be explored are: early and late penumbral salvage, early and late collateral flow enhancement, and early and late infarct growth.

E.3.5.2. Exploratory Clinical Efficacy Endpoints

This study is underpowered to definitively determine efficacy, so all clinical efficacy analyses will be purely exploratory and descriptive. Four clinical outcome measures were selected based on their reliability, familiarity to the neurologic community, and adaptability for use in patients who have had a stroke. These endpoints are: the modified Rankin Scale (mRS), a rating of global disability; the Barthel Index (BI), a measure of instrumental activities of daily living; the National Institutes of Health Stroke Scale (NIHSS), a measure of neurologic deficit severity; and the EuroQol (EQ-5D), an assessment of health-related quality of life; and AMC Linear Disability Scale, a granular degree of disability.

Clinical efficacy endpoints will be characterized in the active and sham patients, and in higher and lower dose tiers. Early course clinical efficacy endpoints of greatest interest that will be explored are: **1)** Normalized change in neurologic deficit from baseline to 24h (normalized delta NIHSS – linear variable, analyzed with means and 95% CIs; and **2)** Degree of neurologic deficit at 24h (NIHSS – quasi-linear variable, analyzed with means and 95% CIs). Final outcome clinical efficacy endpoints of greatest interest that will be explored are: **1)** Degree of disability at 90 days, assessed across all 7 levels of the modified Rankin Scale – ordinal variable, analyzed with medians (IQRs) and means (95% CIs); **2)** Functional independence (mRS 0-2) at 90 days – binary variable, analyzed with rates and 95% CIs; **3)** Granular degree of disability at 90 days (AMC Linear Disability Scale) – linear variable, analyzed with means and 95% CIs; and **4)** Health-related quality of life (EQ-5D) – linear variable, analyzed with means and 95% CIs.

References:

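### D.6.9 builds penumbral salvage as a volume although Aim III defines it as a proportion, and the exploratory salvaged-volume and 24-hour NIHSS summaries make no use of baseline values already collected (low priority)

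*Combined protocol and SAP*

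**What the plan says.** **Scale of penumbral salvage**

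- Section A, Specific Aim III: early and late salvage is "defined as proportion of penumbral tissue on baseline multimodal MRI that does not proceed to infarct", assessed at 2 and 24 hours.
- D.6.9 Imaging Assessments: the 2-hour measure is "Early penumbra preservation: Volume of baseline penumbra tissue not progressing to ischemic core at 2h" and the 24-hour measure is "Penumbral salvage: Volume of baseline penumbra tissue not progressing to ischemic core at 24h". Both are volumes. The same section quantifies baseline penumbra volume as perfusion volume minus core volume.
- E.3.5.1: "The six imaging efficacy endpoints of greatest interest that will be explored are: early and late penumbral salvage", followed by collateral flow enhancement and infarct growth. No unit or scale is printed. The parent heading, E.3.5, carries the tag for Specific Aim 3.

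**Use of baseline values**

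- E.3.5.1: the imaging "endpoints will be characterized in the active and sham patients, and in higher and lower dose tiers, using means and 95% confidence intervals".
- E.3.5.2: the 24-hour NIHSS is a "quasi-linear variable, analyzed with means and 95% CIs". A companion endpoint, normalized change in NIHSS from baseline to 24 hours, is listed first; its formula is not printed.
- D.6.2 collects baseline NIHSS. E.2.2 compares baseline characteristics between arms, but no adjusted model appears anywhere in the plan. E.2.2 also classes NIHSS among ordinal or non-normal variables, summarised by medians and interquartile ranges.

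E.3.5.1 and E.3.5.2 declare all these analyses exploratory and descriptive.

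**The concern.** An analyst working from D.6.9 would average millilitres; one working from Aim III would average proportions. The two can rank results differently: 50 mL saved out of 100 mL is more volume but a smaller proportion (50%) than 30 mL out of 40 mL (75%). An unprinted scale also leaves room to choose it after the data are seen.

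Raw salvaged volume tends to grow with baseline penumbra. That can vary widely here, because D.3.1 admits occlusions from the ICA to M3/M4, ACA, PCA and PICA and asks only for a mismatch ratio of at least 1.2. Similarly, the 24-hour NIHSS is likely to depend on the baseline score. With 6 to 12 sham patients, chance differences at baseline feed directly into raw means.

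The stake is modest. These endpoints matter because D.6.10.2 rests the choice of the next trial on the outcome measures taken together.

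**Working it through.** **Sample size (E.2.1).** 6 tiers × (3 active + 1 sham) = 24, that is 18 active and 6 sham. With every tier expanded once, 6 × 8 = 48, that is 36 and 12. The plan's range of 24 to 48 is reproduced.

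**Chance imbalance.** The SD of the active-sham difference in a baseline variable, in units of its own SD, is √(1/n_sham + 1/n_active).

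- 6 vs 18: √(1/6 + 1/18) = 0.47; the chance of exceeding 0.5 SD is 29%.
- 12 vs 36: √(1/12 + 1/36) = 0.33; the chance is 13%.

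**Do the scales disagree?** The documents give no penumbra or salvage figures, so these are assumed: mean penumbra 60 mL, coefficient of variation 0.4 to 1.0, sham salvage 50%. With no true effect, volume and proportion gave arm differences of opposite sign in 26–39% of simulated trials. With a true 15-point benefit they did so in 13–25% at N=24 and 7–20% at N=48.

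**Which summary points the wrong way?** Assumed: lognormal penumbra P; salvaged proportion S with mean 0.65 active vs 0.50 sham and SD 0.25, unrelated to P; salvaged volume V = P × S plus normal error. Entries are the percentage of 200,000 trials with active below sham, in the order raw V / V÷P / V adjusted for P.

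| Penumbra mean (SD), mL | Error SD, mL | 18 vs 6 | 36 vs 12 |
|---|---|---|---|
| 50 (20) | 0 | 17.4 / 10.3 / 12.2 | 9.8 / 3.5 / 4.7 |
| 50 (20) | 5 | 18.3 / 12.9 / 14.0 | 10.6 / 5.3 / 5.9 |
| 50 (20) | 10 | 20.8 / 18.3 / 18.0 | 12.9 / 10.2 / 9.3 |
| 50 (40) | 0 | 24.3 / 10.4 / 15.2 | 18.6 / 3.6 / 7.3 |
| 50 (40) | 5 | 25.0 / 16.2 / 16.8 | 19.1 / 8.3 / 8.7 |
| 50 (40) | 10 | 26.1 / 24.5 / 20.3 | 20.2 / 17.2 / 11.8 |
| 25 (25) | 0 | 26.1 / 10.1 / 16.4 | 21.3 / 3.6 / 8.7 |
| 25 (25) | 5 | 27.7 / 28.4 / 21.7 | 22.7 / 21.7 / 13.1 |
| 25 (25) | 10 | 30.8 / 37.4 / 28.8 | 25.7 / 33.4 / 20.6 |

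Adjusted volume beats raw volume in all 18 cells, with a standard error 0.50 to 0.86 of raw. The proportion is best without error, but can be worse than raw volume when penumbras are small and error is present. For example, a 10 mL core at ratio 1.2 leaves 12 − 10 = 2 mL of penumbra, so a 1 mL error moves the proportion by 50 points.

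**Unfavourable case.** If the mean salvaged proportion falls by 0.15 to 0.30 per log unit of P, adjusted minus raw runs from −4.3 points (7.7% vs 12.0%) to +1.0 point (29.9% vs 28.9%), and the standard-error ratio is 0.75 to 0.99. At the steep end nothing is gained.

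**24-hour NIHSS.** Adjusted over raw standard error is √[(1 − r²)(1 + 1/(N − 4))], with r the assumed baseline-to-24-hour correlation. At N=24 and r = 0.5 this is √(0.75 × 1.05) = 0.89. A plain change score with equal variances gives √(2 − 2r).

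| r | Adjusted, N=24 | Adjusted, N=48 | Change score |
|---|---|---|---|
| 0 | 1.02 | 1.01 | – |
| 0.3 | 0.98 | 0.97 | 1.18 |
| 0.5 | 0.89 | 0.88 | 1.00 |
| 0.7 | 0.73 | 0.72 | 0.77 |
| 0.8 | 0.61 | 0.61 | 0.63 |

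A plain change score therefore does not replace adjustment at low correlation. The r = 0 row gives the cost of an uninformative covariate.

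**The case against.** - **The scale can be inferred.** E.3.5 is tied to Specific Aim 3 and uses that aim's term, so the proportion is arguably inherited and D.6.9 lists its numerator. This largely stands. A reader might infer that the endpoint is undefined or that the proportion cannot be recovered. The documents do not support that, because baseline penumbra volume is quantified and the proportion is one division away. What remains is conflicting wording in D.6.9 and an unprinted scale in E.3.5.1.
- **Adjustment is a preference.** E.3.5 plans to describe groups, with no test or model. This stands too: the adjusted differences are an inexpensive addition, not the repair of an error.
- **Baseline NIHSS is already used.** It is, in the normalized change, but only as a change score. The raw 24-hour score has no counterpart that conditions on baseline.
- **NIHSS is not normal.** E.2.2 says as much. A linear-model interval with as few as 6 sham patients needs a bootstrap or rank-based safeguard.
- **The inputs are assumed.** They are, because the documents give none; hence the ranges and the unfavourable case.

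**Conclusion.** The point holds at low priority. The conflict between Aim III and D.6.9 is certain from the text. The benefit of adjustment depends on assumed inputs: a standard error 0.50 to 0.86 of raw for salvaged volume when the salvaged proportion is unrelated to penumbra size, and 0.98 to 0.61 of raw for 24-hour NIHSS (N=24, r from 0.3 to 0.8).

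Three stronger readings should be resisted.

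- A reader might infer that the unadjusted active-sham comparison is biased. It is not: the arms are randomized 3:1, so the loss is of precision. That reasoning does not extend to higher versus lower tiers, which fill in sequence (E.2.3.1) and are not randomized against each other.
- A reader might infer that the proportion is the more reliable measure. The table shows it is not always so; the reason to adopt it is consistency with Aim III.
- A reader might infer that the trial's decisions are compromised. No safety, escalation, tolerability, feasibility or sample-size rule uses these endpoints.

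**What to change.** 1. **D.6.9:** define early and late penumbral salvage as the salvaged volume at 2 and 24 hours, respectively, divided by baseline penumbra volume.
2. **E.3.5.1:** state that this proportion is reported by arm with a 95% CI. As an exploratory supplement, report the active-sham difference in salvaged volume from a linear model with baseline penumbra volume as covariate, with a 95% CI.
3. **E.3.5.2:** keep the planned summaries. Add the active-sham difference in 24-hour NIHSS adjusted for baseline NIHSS, with a 95% CI, using a bootstrap interval or a rank-based check.
4. **E.3.5.1 and E.3.5.2:** label higher-versus-lower tier summaries as non-randomized comparisons.

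This changes wording and adds two small models. It needs no new data and leaves the sample size unchanged. The price is one model term per contrast: about 2% in standard error at N=24 and 1% at N=48 if the covariate proves uninformative. The proportion will be unstable in patients with a very small penumbra, which is why the adjusted volume should stand beside it.

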We will implement a traditional 3+3 (rule-based, modified Fibonacci) dose escalation design, with 3:1 randomization to active treatment vs sham control. There will be 6 dose tiers, reflecting increasing intensity and duration of stimulation: Tier 1 – 1 mA, single 20 - min cycle; Tier 2– 2 mA, single 20 min cycle; Tier 3 – 1 mA, 2 cycles of 20 min/20 min off; Tier 4– 2 mA, 2 cycles of 20 min/20 min off; Tier 5 – 1 mA, 3 cycles of 20 min/20 min off; Tier 6 – 2 mA, 3 cycles of 20 min/20 min off (Figure 7). Patients in the sham stimulation arm at all the tiers will have the cap and electrodes in place, and switches moved but without any delivered electrical stimulation. While the highest dose tier in this study is expected to be fully safe, based on preclinical and clinical studies^{12,19}, since this is a first-in-human study in acute stroke, a formal escalation to higher dose tiers is prudent.

Figure 7. This figure shows the 6 escalating tiers. Blue represents 1 mA and purple shows 2 mA of tDCS. Symptomatic ICH (SICH) in none of the three patients in a tier will result in escalation. However, SICH in one patient, 3 more patients and 1 sham will be enrolled at the same tier.

D.4. Management during and post stimulation period

Figure7: Technician-filled tolerability form	Presence		Severity		Effect on the study treatment (Shortened the stim duration)		Duration/Frequency			Treatment			
	A	P	M	Mod	S	Y	N	< 50 % of stim period	≥50% of stim period	lasted after stim period (min)	None	Con	Med
Adverse Events													
Rash													
Skin dryness													
Hair loss													
Itching													
Hives													
Skin Sensitivity to light													
Skin soreness													
Skin redness													
Skin darkening													
Numbness													
Tingling													
Dizziness													
General Pain													
Headache													

*A=Absent, Con=Conservative therapy such as cold pack and lotion, M= Mild, Mod=Moderate, Med=Medication such as topical steroid, N= No, P= Present, R: Resolved, S: Severe, Stim= Stimulation, Y=Yes.

Figure 8. Shows the technician-filled tolerability form. The selected items are based on the most common reported adverse effects associated with tDCS.

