After randomization and during the stimulation, all patients will be monitored closely by a physician-investigator. NIHSS will be obtained at the end of each 20-minute stimulation cycle and a visual inspection of the skin and rate degree of any potential erythema under the electrode will be performed. Then, a tolerability form will be completed based on validated cutaneous, neurological, and pain items of the PRO-CTAE (Patient-Reported Outcomes version of the Common Terminology Criteria for Adverse Events) (Figure 8).^{49,50}

After the stimulation, nursing neurologic assessments will be performed by Neurointensive Care Unit or Stroke Unit nurses with extensive experience in monitoring acute stroke patients. Specifically, patients will be monitored for any signs of neurological worsening and will be queried on development of new or worsening neurological symptoms including headache, dizziness, numbness, or weakness, etc. If any sign or symptom of neurological worsening is suspected, the patient will be immediately assessed by the on-call neurologist and an immediate brain imaging (CT or MRI) will be obtained. Neuro-checks will be performed at 1h and 2h after stimulation and then every 2 hours in patients requiring Neurointensive Care and every 4 hours in patients requiring Stroke Unit Care. Subsequent care will be continued in these settings, including medical management per national guidelines for acute ischemic stroke management issued by the American Stroke Association.⁵¹ Patients will not receive NSAIDs as concomitant therapy for the first 7 days after enrollment. All patients will undergo a multimodal MRI or CT including standard parenchymal images, non-invasive angiography, and perfusion studies and formal NIHSS assessment at 2-hour and 24-hour following the end of the stimulation tier as part of the study protocol.

D.6. Study Visits and Data Acquisition

D.6.1 Schedule of Events

	Baseline	End of each 20-min stimulation cycle			2-hr	24-hr	Day 4	Day 30	Day 90
		1	2	3					
Consent	✓								
History / Exam	✓								
Routine Labs	✓								
Vital Signs	✓	✓	✓	✓					
Patient tolerability form		✓	✓	✓					
Technician tolerability form/Skin Inspection*	✓	✓	✓	✓					
Multimodal MRI or CT	✓				✓	✓			
NIHSS	✓	✓	✓	✓	✓	✓			✓
Modified Rankin Scale (mRS)	✓						✓	✓	✓
Barthel Index (BI)									✓
EuroQol (EQ-5D)									✓
AMC Linear Disability Scale									✓
Interval serious adverse events		✓	✓	✓	✓	✓	✓	✓	✓

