The lead safety endpoint adverse event is symptomatic intracranial hemorrhage (SICH), defined using the SWIFT PRIME trial criteria⁵⁵: an increase of 4 or more points on the NIHSS within 24 hours of stimulation associated with parenchymal hematoma type 1 (PH1), parenchymal hematoma type 2 (PH2), remote intraparenchymal hemorrhage (RIH), subarachnoid hemorrhage (SAH), or intraventricular hemorrhage (IVH). In addition, all hemorrhages, both symptomatic and asymptomatic, will also be separately classified and analyzed by radiologic subtype, as hemorrhagic infarction type 1 (HI1), hemorrhagic infarction type 2 (HI2), PH1, PH2, RIH, SAH, or IVH.⁵⁵ A central neuroimaging core lab, blinded to treatment assignment, will review all brain MRI scans obtained at 24h and rate presence and type of radiologic hemorrhagic transformation. In addition, in patients who experienced worsening by 4 or more NIHSS points in the first 24 hours, they will review any and all additional brain MRI or CT scans obtained during the 24h time period,

SICH is the primary safety endpoint of the current trial, but trial results will be assessed on a variety of additional safety, feasibility, and tolerability results as well. It is anticipated that, after completion of the current trial, the judgement of whether to proceed directly to a pivotal trial, to proceed to a larger safety and preliminary efficacy trial, or to not proceed with further development, will rest on a considered and informed assessment of all outcome measures. It is important therefore to collect data on a wide range of safety

endpoints and a wide range of measures of functional outcome, as is planned in this proposal. In making the selection of a primary safety endpoint, an emphasis was placed on ensuring patient safety throughout the course of the trial by choosing an endpoint with uncontested clinical relevance (Symptomatic Intracranial Hemorrhage).

D.6.10.3 Additional Adverse Events with Specific Interrogation

In addition to general screening for all serious adverse events and focused elicitation of symptomatic intracranial hemorrhage events, the following events will be specifically interrogated for and recorded in the case report forms: skin redness, scalp rash, hair loss, seizure, headache, sensitivity to light, new ischemic stroke, deep venous thrombosis, pulmonary embolism, pneumonia, acute MI.

E. Safety Monitoring

E.1. Data and Safety Monitoring Plan

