For the final statistical analysis of the primary SICH safety endpoint, a chi-square test will be used to detect differences in the rate of SICH between the active treatment and sham patients and higher and lower dose tiers. The treatment will be considered to have exhibited adequate safety in the current trial to proceed to future, larger, pivotal efficacy trials if tDCS results in lower or equivalent rates of SICH compared to sham.

E.2.3.3. Secondary Safety Endpoints Analysis

In secondary safety endpoint analyses, the following will be compared between the active treatment and sham patients, and between higher and lower dose tiers, using chi-squared tests: **1) Asymptomatic ICH by 24h** (intracranial hemorrhage not associated with NIHSS worsening ≥ 4); **2) Early neurologic deterioration** (worsening ≥ 4 on NIHSS during the 24-hour period after stimulation, with or without intracranial hemorrhage); **3) All-cause mortality at day 90 (mRS);** and **4) All serious adverse events.**

E.3.3. Tolerability Endpoint Analysis

The lead tolerability endpoint is completion of the protocol-assigned stimulation treatment without early cessation due to cutaneous, neurologic, nociceptive or other adverse effects. Experience with tDCS in post-stroke patients indicates only infrequent cutaneous (itching, tingling) adverse effects are likely to occur. Accordingly, for the current study, a patient will be considered to have tolerated the procedure if at least 75% of the stimulus period was completed. The treatment will be considered generally tolerable if, among all enrolled patients, tolerated procedures are achieved in $\geq 90\%$ of patients, assessed with a one-sided p value of 0.025. Secondary tolerability endpoints will be the

rate and severity of cutaneous, neurological, and pain items of the technician-filled (Figure 7) and patient-filled tolerability forms ⁴⁹, descriptively compared between active treatment and sham patients, and between higher and lower dose tiers.

E.3.4. Feasibility Endpoint Analysis (Specific Aim 2)

A time-motion analysis and mock run-throughs will be conducted prior to first enrollment. Nonetheless, it is anticipated that processes to optimize rapid placement of the cap and electrodes will continue to improve with experience gained from initially enrolled patients. The predefined success threshold for feasibility will be median time from randomization to tDCS initiation \leq 10 minutes in the last 10 enrolled patients.

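### Late-onset non-serious skin reactions have no scheduled collection point after the last stimulation cycle, and the patient tolerability form has no baseline

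*Combined protocol and SAP*

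**What the plan says.** - **Promise.** D.6.10.3 states that "the following events will be specifically interrogated for and recorded in the case report forms: skin redness, scalp rash, hair loss, seizure, headache", then continues with light sensitivity and several medical events such as pneumonia, venous thrombosis and myocardial infarction. It presents this as additional to serious adverse event screening. It names no visits.
- **Patient form.** In D.6.1 the row "Patient tolerability form" is ticked at the end of cycles 1, 2 and 3 only. It is blank at baseline and from 2 hours onward.
- **Technician form and skin.** The row "Technician tolerability form/Skin Inspection" is ticked at baseline and at the end of each cycle, and is blank from 2 hours onward. Its footnote reads "Skin Inspection will be performed before each stimulation period".
- **Visit lists.** The two forms appear only in D.6.3, as "Tolerability/AE Form – Technologist, Tolerability Questionnaire – Patient". They are absent from D.6.2 (baseline) and from D.6.4 to D.6.8.
- **Follow-up events.** From 2 hours to day 90 the only adverse-event row is "Interval serious adverse events". D.6.10.1 likewise limits 90-day recording to serious events.
- **Technician form content.** The form in D.4 lists hair loss, skin darkening, light sensitivity, numbness, tingling, dizziness and headache. One column is headed "lasted after stim period (min".
- **Analysis.** E.3.3 makes the "rate and severity of cutaneous, neurological, and pain items of the technician-filled (Figure 7) and patient-filled tolerability forms" secondary tolerability endpoints, described by arm and by higher versus lower tier.

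**The concern.** D.6.10.3 and the schedule do not meet. The text commits to asking about non-serious skin effects, but after the last cycle no form, inspection or visit item would record one. Hair loss and skin darkening in particular may not show while the session is still running. The follow-up conditions in the same D.6.10.3 list suggest that the list was not meant for the stimulation session alone. C.3 describes skin erythema as a mild dose-dependent effect of this technique, so the omission bears on a dose-escalation study.

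At the other end, Hypothesis I-c refers to pain, discomfort and skin changes that are related to stimulation. For patient-reported items nothing in the plan supplies that attribution. There is no answer before stimulation, E.3.3 has no new-or-worse rule, and the causality assessment in E.1 is stated for serious events only. Numbness, dizziness and headache can be symptoms of the qualifying stroke.

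At stake is how far the secondary tolerability results can be interpreted. The data safety board sees these among other safety outcomes, and D.6.10.2 says that later development decisions will weigh all outcome measures.

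**Working it through.** No stated figure of the plan rests on this point, so the check is mainly a comparison of sections, with some arithmetic for context.

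**1. Collection points, by item (D.6.1, D.6.2 to D.6.8, D.4)**

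| Item | Before stimulation | End of each cycle | 2 h to day 90 |
|---|---|---|---|
| Patient form | none | yes | none |
| Technician form / skin inspection | ticked, but not listed in D.6.2 | yes | none |
| Non-serious skin events named in D.6.10.3 | skin inspection only | yes, through the forms | none in the schedule |
| Headache, dizziness, numbness | technician form, if the tick covers the whole form | yes | asked by nurses at 1 h, 2 h, then every 2 or 4 h; route to the case report form not stated |
| Serious events | not applicable | yes | yes |

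**2. Length of the scheduled window.** Inputs from D.4: k cycles of 20 minutes, taken here with 20 minutes off between cycles. Time from start of stimulation to the last form = 20k + 20(k − 1).
- Tiers 1 and 2, k = 1: 20 + 0 = 20 minutes, one form.
- Tiers 3 and 4, k = 2: 40 + 20 = 60 minutes, two forms.
- Tiers 5 and 6, k = 3: 60 + 40 = 100 minutes, three forms.

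**3. Arm sizes.** E.2.1 gives 24 to 48 patients. This reproduces: 6 × (3 + 1) = 24 and 6 × (6 + 2) = 48. Sham is therefore 6 × 1 = 6 to 6 × 2 = 12 if all six tiers are run.

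**4. What sham can correct.** With zero reports among n sham patients, the one-sided 95% upper bound on the true rate is 1 − 0.05^(1/n).
- n = 6: 39%.
- n = 12: 22%.

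A background symptom rate anywhere below these bounds would be compatible with a sham arm that reports nothing.

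**5. Tier comparison.** The documents give no background rate of stroke-related symptoms, so p is an assumption. If each form independently has chance p of such a report, the chance of at least one report per patient is 1 − (1 − p)^k.

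| p (assumed) | 1 form | 2 forms | 3 forms |
|---|---|---|---|
| 0.10 | 10% | 19% | 27% |
| 0.20 | 20% | 36% | 49% |
| 0.30 | 30% | 51% | 66% |

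So a per-patient rate could rise with tier without any stimulation effect. Independence makes this an extreme case. A constant symptom reported on every form gives p in each column and no trend, and E.3.3 does not say whether rates are per patient or per form.

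**The case against.** The strongest reply is that the plan covers more than the schedule table suggests. Much of it stands.

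- The technician row is ticked at baseline, and that form carries numbness, tingling, dizziness and headache. The footnote speaks only of skin, so it is unclear whether the tick covers the whole form.
- After stimulation, nurses ask about new or increasing headache, dizziness and numbness. Headache is the pain item in the D.6.10.3 list, so the clear gap is skin.
- The technician form has a field for how long an effect persisted afterwards, so some observation beyond the end of current was intended. It serves a reaction already present, not one that starts later.
- A late reaction that meets the serious definition is recorded to day 90.
- D.6.10.3 may be read as a commitment across follow-up that the table simply fails to repeat. Even so, staff working from the table and visit lists would not be prompted to ask.
- The patient form is not reproduced. Its wording may already ask about new symptoms only.

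A reader might infer that stroke symptoms will be counted as stimulation effects. The documents do not support that. The lead tolerability endpoint is completion of at least 75% of stimulation and is not scored from the forms. The form items are compared descriptively with a randomized sham arm, in which pre-existing symptoms are expected at the same rate, so the between-arm result is noisier but not biased by them. Nor does it size the defect to say that one report moves the sham rate by 1/6 and the active rate by 1/18, because that holds for any yes/no item in samples this small.

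**Conclusion.** The point holds in a limited form. Late-onset non-serious skin reactions have no scheduled collection point after minute 20, 60 or 100, according to tier, in any enrolled patient. Symptoms on the patient form cannot be separated within a patient into pre-existing and new, unless the unseen form does this by its wording. The second gap adds noise to a descriptive secondary comparison, and a sham arm of 6 to 12 corrects for it only imprecisely.

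The size of any undercount or overcount cannot be given, because the documents state neither a rate of delayed skin effects nor a baseline symptom rate. The tier figures above rest on an assumed p and on independence between forms.

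A reader might also infer that escalation decisions or the tolerability success criterion are compromised. They are not: the formal escalation rule uses symptomatic intracranial hemorrhage, and the success criterion uses completion of stimulation. This is an inexpensive improvement that should be made, since the missing observations cannot be recovered afterwards, but it does not threaten the trial's main conclusions.

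**What to change.** 1. **Baseline.** In D.6.1 and D.6.2, add the patient tolerability form at baseline, before randomization, where the patient can answer. State that the technician baseline tick covers the full form. In E.3.3, report secondary tolerability items as new or worse than baseline.
2. **Early follow-up.** In D.6.1, D.6.4 and D.6.5, add both tolerability forms and the skin inspection to the existing 2-hour and 24-hour visits.
3. **Interval row.** In D.6.1 and D.6.4 to D.6.8, extend the interval adverse-event item at 2 hours, 24 hours, day 4, day 30 and day 90 to include the D.6.10.3 events. The day 30 contact is by phone, so skin items there would rest on the patient's report.

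**Cost.** One short form before randomization, which leaves the randomization-to-initiation time of E.3.4 untouched, and a few minutes at visits that already take place. Self-report will be missing for some aphasic or stuporous patients, whom D.3.2 expects to enroll. Observed rates of mild skin effects may rise because they are being looked for.
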